6.6.1 Evaluation of Toxicity

All participants will be evaluable for toxicity from the time of their first treatment. All toxicities will be monitored closely.

Development of grade III-IV treatment related toxicity will be monitored closely. If we observe 3 or more patients with grade III-IV treatment related toxicity, the study will be terminated.

7. DOSING DELAYS/DOSE MODIFICATIONS

All adverse events experienced by participants will be collected from the time of the first dose of study treatment, through the study and until the final study visit. Participants continuing to experience toxicity at the final study visit may be contacted for additional assessments until the toxicity has resolved or is deemed irreversible.

There will be no dosing delays/modifications.

8. RISKS AND DISCOMFORTS

8.1 Drug side effects and toxicities

Potential side effects with dexamethasone 0.5mg/5mL solution used as an oral topical rinse include an increased risk of developing oropharyngeal candidiasis and systemic absorption. All patients will be prescribed antifungal prophylaxis while on study with either fluconazole, clotrimazole or nystatin (see

CONFIDENTIAL

This document is confidential. Do not disclose or use except as authorized.

section 5.5). All participants will be informed that they may withdraw from the study at any time. As a topically applied agent, dexamethasone therapy can be discontinued at any time without any complications. Any noted clinical response will be expected to be reversed in such situations.

Prolonged application of potent topical corticosteroids (e.g., > 50 g of clobetasol propionate or > 500 g of hydrocortisone per week) may lead to short-term hypothalamic-pituitary-adrenal axis alteration. In our study, in case of any systemic absorption, the maximum dose would be 10.5 mg/week (5 mL x 0.1 mg/mL = 0.5 mg/rinse, 3 times/day = 1.5 mg, 7 days/week = 10.5 g). We do not expect there to be significant systemic absorption, and therefore do not expect systemic side effects of dexamethasone solution when used as a swish and spit. Mucolox™ is a vehicle for drug delivery used in compounding medications with ingredients expected to be harmless (see section 11.1.1).

9. POTENTIAL BENEFITS

9.1 Potential benefits for participating individuals

All subjects will be assigned an active treatment. Thus, it is anticipated that the majority of participants may benefit from participation in this study. Additionally, most participants may benefit from the satisfaction in knowing that their involvement has a potential impact on the clinical care of future patients suffering from their condition.

9.2 Potential benefits to society

The results of this study have the potential to impact clinical guidelines for the management of oral lichen planus.

10. MONITORING AND QUALITY ASSURANCE

10.1 Safety monitoring

The safety of participants and the overall study will be monitored continuously throughout the study period. At the 4 week visit, evaluating physicians will review the participants' diaries for self-reported adverse events. Subjects will be instructed to contact their treating physician by phone or email or patient Gateway to report any unexpected side effects or side effects lasting more than 7 days, should they occur. Any necessary medical intervention will be handled by the treating physician. Data accuracy and protocol compliance will be monitored and assured by the Principal Investigator and toxicities will be reported promptly to the IRB (see below).

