5.5 General Concomitant Medication and Supportive Care Guidelines

There will be no restrictions on concomitant medications or supportive care measures.

All subjects will be treated with fluconazole 200 mg tablets once-a-week dosing for prophylaxis as topical steroid therapy may increase the risk of candidiasis. This is typically very effective at preventing candidiasis in susceptible patients, and since there are no interim clinical visits, this will minimize the risk of secondary infection, which if not detected early, could confound the results at the week 4 evaluation. A single weekly dose of fluconazole is not sufficient to have an impact on therapeutic levels of other medications. Fluconazole is a pregnancy category D drug. A such, pregnant women will be excluded from this study.

Any subjects that are already taking a systemic antifungal medication at the time of study enrollment will continue their prescribed medication and will not need to take the additional weekly fluconazole dose.

Clotrimazole or nystatin will be prescribed as an alternative antifungal drug in the event of fluconazole

CONFIDENTIAL

This document is confidential. Do not disclose or use except as authorized.

allergy. Clotrimazole 10 mg troche (lozenge) to be dissolved in the mouth four times a day for four weeks; or nystatin 100,000 unit/mL oral suspension to rinse for one minute, swish and spit, four times a day for four weeks.

Possible side effects of fluconazole include nausea, vomiting and headache. Possible side effects of nystatin oral suspension include rash, diarrhea, nausea, oral irritation, vomiting. Possible side effects of clotrimazole troche (lozenge) include abnormal sensation in the mouth, loss of appetite, diarrhea, nausea, vomiting, abnormal liver function tests.

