6.3.1 Monitoring of Adverse Events

All adverse events will be reviewed by the principal investigator or covering clinician. In accordance with PHRC guidelines, the PI or covering clinician will determine whether an adverse event was expected and/or related to study procedures. Study subjects will be asked to report any adverse events or concerns to study staff as they arise.

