10.4 Expected Toxicities

A list of the adverse events and potential risks associated with the agents administered in this study appear above and will determine whether dose delays and modifications will be made or whether the event requires expedited reporting **in addition** to routine reporting.

Some expected toxicities include: transient burning, and the development of secondary oral candidiasis (which will be minimized with prophylactic antifungal drug therapy).

Prolonged application of potent topical corticosteroids (e.g., > 50 g of clobetasol propionate or > 500 g of hydrocortisone per week) may lead to short-term hypothalamic-pituitary-adrenal axis alteration³³. In our study, in case of any systemic absorption, the maximum dose would be 10.5 mg/week (5 mL x 0.1 mg/mL = 0.5 mg/rinse, 3 times/day = 1.5 mg, 7 days/week = 10.5 g). We do not expect there to be significant systemic absorption, and therefore do not expect systemic side effects of Mucolox™ and/or dexamethasone solution when used as a swish and spit.

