12.1 Monitoring and quality assurance

Safety monitoring

The safety of participants and the overall study will be monitored continuously throughout the study period. Evaluating physicians will query participants for any adverse events and review self-reported adverse events. Subjects will be instructed to contact their treating physician by phone or email to report any unexpected side effects or side effects lasting more than 7 days, should they occur. Any necessary medical intervention will be handled by the treating physician. Data accuracy and protocol compliance will be monitored and assured by the Principal Investigator and toxicities will be reported promptly to the IRB (see above).

CONFIDENTIAL

This document is confidential. Do not disclose or use except as authorized.

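### Sections 6.3.1 and 10.1/12.1 give patients different rules for reporting side effects; under the narrower one, short expected events of any grade may surface only at week 4, which slows the toxicity stopping rule

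*Combined protocol and SAP*

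**What the plan says.** Two reporting instructions appear.

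- Section 6.3.1 (Monitoring of Adverse Events): "Study subjects will be asked to report any adverse events or concerns to study staff as they arise".
- Section 10.1 (Safety monitoring): patients contact the treating physician "to report any unexpected side effects or side effects lasting more than 7 days, should they occur". Section 12.1 repeats this threshold: "report any unexpected side effects or side effects lasting more than 7 days, should they occur".

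Other events are to be picked up by the study team. Section 10.1 has physicians review the participants' "diaries for self-reported adverse events" at the 4-week visit. Section 12.1 adds: "Evaluating physicians will query participants for any adverse events and review self-reported adverse events", with no date. The visit schedule in section 5 has only Day 1 and Day 28 ± 5.

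Three other passages bear on this.

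- Section 6.6.1: "If we observe 3 or more patients with grade III-IV treatment related toxicity, the study will be terminated".
- Section 10.4: "Some expected toxicities include: transient burning, and the development of secondary oral candidiasis".
- Section 5.5 justifies weekly fluconazole by the absence of interim visits, and says of secondary infection: "which if not detected early, could confound the results at the week 4 evaluation".

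**The concern.** The two instructions differ in what is reported, when, and to whom. Section 6.3.1 covers everything, at once, to study staff. Sections 10.1 and 12.1 set a threshold and name the treating physician. The threshold looks at novelty and duration but not at severity, and it leaves the patient to judge what counts as expected.

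The stopping rule can act only on events the team knows about. If a patient has severe burning for a few days and has been given the 10.1 instruction, nothing in that instruction prompts a call. The event then waits for the diary review at the last visit, while other patients continue to be enrolled.

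A smaller matter is candidiasis. The plan itself says that infection found late could confound the week-4 result, yet it also lists candidiasis as expected, so its first 7 days fall below the 10.1 threshold.

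**Working it through.** **Inputs from the protocol.** 24 patients and about 5 per month (6.2); final visit on Day 28, window Day 23 to Day 33 (section 5 schedule); stop at 3 patients with grade III-IV related toxicity (6.6.1). **Assumed, not in the protocol:** true rates of such toxicity of 5%, 10%, 20% and 30%; even accrual; onset uniform over the 28 days of treatment.

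**1. The plan's own figure.** 24 / 5 = 4.8 months, which agrees with the stated five months or so. With 30.44 days per month, one patient enters every 30.44 / 5 = 6.09 days.

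**2. Which events the narrower rule holds back.** Its two triggers are joined by *or*, so an event escapes only if it meets neither.

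| | 7 days or less | more than 7 days |
|---|---|---|
| Unexpected | reportable at once | reportable at once |
| Expected | **not reportable before the visit** | reportable after day 7 |

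Grade does not enter the table. Under 6.3.1 all four cells are reportable at once.

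**3. Worst case for the stopping count.** Suppose the first three patients each have a short, expected grade III related event on their Day 1, and none calls. With the first entry at study day 0, the third patient enters at 2 × 6.09 = 12.2. Her final visit is at 12.2 + (23, 28 or 33) − 1 = study day 34, 39 or 44. The number started by study day t is floor(t / 6.09) + 1, which gives 6, 7 or 8. That is 3, 4 or 5 patients beyond the third. Under 6.3.1 the third event would be known on about day 12.

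For comparison, an expected event that persists is delayed by about 7 days under 10.1. This corresponds to 7 / 30.44 × 5 = 1.1 enrolments.

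**4. Average over trials.** 100,000 simulated trials, stopping at the third reported case. Every case is treated as hidden until the visit, which is pessimistic because only short expected events would be. Mean number enrolled when the rule fires, among trials that reach three cases:

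| Toxicity rate | P(3 or more of 24) | Reported at onset | At day 28 | At day 33 | Extra enrolled |
|---|---|---|---|---|---|
| 5% | 0.12 | 19.2 | 20.8 | 21.3 | 1.6 to 2.1 |
| 10% | 0.44 | 17.9 | 19.6 | 20.3 | 1.7 to 2.4 |
| 20% | 0.89 | 14.7 | 16.7 | 17.6 | 2.0 to 2.9 |
| 30% | 0.99 | 11.6 | 13.7 | 14.7 | 2.1 to 3.1 |

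The chance of reaching three cases is the same whenever they are reported. What changes is the chance of stopping before all 24 are enrolled. With reporting at onset, day 28 and day 33, it is 0.09, 0.07 and 0.06 at a 5% rate; 0.36, 0.30 and 0.27 at 10%; 0.83, 0.77 and 0.73 at 20%; and 0.97, 0.95 and 0.94 at 30%.

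**5. Candidiasis.** An infection passes the 7-day limit before a Day 28 visit only if it starts before about 28 − 7 = Day 21 (Day 16 for a Day 23 visit, Day 26 for a Day 33 visit). Later onset need not be reported before the visit. That last week is also the recall period of the primary endpoint, which uses the worst sensitivity over the past week (5.1.3).

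**The case against.** The strongest reply is that 10.1 and 12.1 do not say *only*, and do not cancel 6.3.1. The recipients differ, so a patient could tell study staff everything and also phone the physician about the events in 10.1. If 6.3.1 is what patients are actually told, there is no delay. That is fair, and the delay arises only where the narrower instruction is the one passed on. But it is the one that appears twice, and nothing says which governs. The Appendix 1 sheet as reproduced carries no side-effect instruction to settle it. The consent pages, which might, were not available to me.

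There are also other routes. Unexpected severe events are reportable under either rule, investigators report serious adverse events under 10.6, and section 5.6 takes patients off treatment if they cannot tolerate the rinse. These narrow the gap, but each depends on staff learning of the event.

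A reader might infer three stronger things that the documents do not support.

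- *That short events and expected events are both held back.* Only events that are both short and expected are, as the table in step 2 shows.
- *That the plan sets a duty of early detection of candidiasis and then defeats it.* Section 5.5 names prophylaxis as the safeguard and sets no such duty. Persistent candidiasis that starts earlier becomes reportable after day 7.
- *That the diary has nowhere to record side effects.* Section 5.2 says adverse effects are recorded there, and the form has a Comments column. The opening rows are missing from the text I have, so I say only that the visible columns include none labelled for side effects.

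**Conclusion.** The contradiction is real and should be corrected. Under the narrower instruction, an expected event of 7 days or less, of any grade, may reach the study team only at the Day 28 ± 5 visit. This can delay the 6.6.1 count by up to about four weeks. The size is 3 to 5 further enrolments in the worst case and about 2 to 3 on average with every case hidden, at assumed toxicity rates of 5% to 30%. The averages rest on even accrual and uniform onset, and they overstate the effect to the extent that some events are unexpected, last longer or are volunteered.

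It might be inferred that the stopping rule cannot work in time. It can: entry is staggered over nearly five months and the count is cumulative, so at a 20% rate the chance of stopping before full accrual falls from 0.83 to 0.77 (0.73 at the edge of the visit window). For candidiasis, the remaining gap is onset in roughly the last week before the score is taken.

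**What to change.** Replace the three passages with one instruction and one recipient. The simplest way is to bring 10.1 and 12.1 into line with the plan's own 6.3.1: any adverse event goes to study staff as it arises. Severe events are then covered whatever their duration or expectedness. In addition:

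- repeat the instruction on the Appendix 1 patient sheet;
- label a diary column for side effects;
- state that the 6.6.1 count is checked whenever a grade III-IV event is reported.

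No change to the stopping threshold, to treatment or to the visit schedule is implied. The cost is a few lines of protocol text, one line on the patient sheet and one diary heading, plus somewhat more calls about minor effects such as brief burning.

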10.2 Adverse events

Adverse event (AE) monitoring and reporting is a routine part of every clinical trial. This study follows Partners Health Care guidelines regarding the definitions and reporting policies of adverse events. The following list of reported and/or potential AEs (Section 10.3) and the characteristics of an Expected Toxicity (Section 10.4) will determine whether the event requires expedited reporting **in addition** to routine reporting.

CONFIDENTIAL

This document is confidential. Do not disclose or use except as authorized.

10.3 Reported and/or potential AE

AE include development of secondary oral candidiasis and short-term hypothalamic-pituitary-adrenal axis alteration (e.g., Cushingoid symptoms), although rare.

10.4 Expected Toxicities

A list of the adverse events and potential risks associated with the agents administered in this study appear above and will determine whether dose delays and modifications will be made or whether the event requires expedited reporting **in addition** to routine reporting.

Some expected toxicities include: transient burning, and the development of secondary oral candidiasis (which will be minimized with prophylactic antifungal drug therapy).

Prolonged application of potent topical corticosteroids (e.g., > 50 g of clobetasol propionate or > 500 g of hydrocortisone per week) may lead to short-term hypothalamic-pituitary-adrenal axis alteration³³. In our study, in case of any systemic absorption, the maximum dose would be 10.5 mg/week (5 mL x 0.1 mg/mL = 0.5 mg/rinse, 3 times/day = 1.5 mg, 7 days/week = 10.5 g). We do not expect there to be significant systemic absorption, and therefore do not expect systemic side effects of Mucolox™ and/or dexamethasone solution when used as a swish and spit.

10.5 Adverse Event Characteristics

- **CTCAE term (AE description) and grade:** The descriptions and grading scales found in the revised NCI Common Terminology Criteria for Adverse Events (CTCAE) version 4.0 will be utilized for AE reporting. All appropriate treatment areas should have access to a copy of the CTCAE version 4.0. A copy of the CTCAE version 4.0 can be downloaded from the CTEP web site http://ctep.cancer.gov/protocolDevelopment/electronic_applications/ctc.htm.
- **Attribution** of the AE:
 - Definite – The AE *is clearly related* to the study treatment.
 - Probable – The AE *is likely related* to the study treatment.
 - Possible – The AE *may be related* to the study treatment.
 - Unlikely – The AE *is doubtfully related* to the study treatment.
 - Unrelated – The AE *is clearly NOT related* to the study treatment.

10.6 Expedited Adverse Event Reporting

10.6.1 Investigators will report to the Overall PI any serious adverse event (SAE) that occurs after the initial dose of study treatment, during treatment, or within 30 days of the last dose of treatment on the local institutional SAE form.

10.7 Expedited Reporting to the Food and Drug Administration (FDA)

CONFIDENTIAL

This document is confidential. Do not disclose or use except as authorized.

The Overall PI, as study sponsor, will be responsible for all communications with the FDA. The Overall PI will report to the FDA, regardless of the site of occurrence, any serious adverse event that meets the FDA’s criteria for expedited reporting following the reporting requirements and timelines set by the FDA.

10.8 Routine Adverse Event Reporting

All Adverse Events **will** be reported in routine study data submissions to the Overall PI on the toxicity case report forms. **AEs reported through expedited processes (e.g., reported to the IRB, FDA, etc.) will also be reported in routine study data submissions.**

11. PHARMACEUTICAL INFORMATION

A list of the adverse events and potential risks associated with the investigational agent administered in this study can be found in Section 10.

11.1 Mucolox™

11.1.1 Description

Mucolox™ (PCCA, Houston, TX 77099) is a mucoadhesive polymer designed to improve mucoadhesion and prolong retention of medications at application sites within the oral mucosa. The composition of Mucolox™ is outlined in the table below.

Ingredient Name	INCI Name/Technical Name	Classification	FDA Reference
Potassium Sorbate NF	Potassium Sorbate	Subpart D – Chemical Preservatives	21 CFR 582.3640
Sodium Benzoate NF	Sodium Benzoate	Subpart D – Chemical Preservatives	21 CFR 582.3733
Glycerin USP (Natural)	Glycerin	Subpart B – General Purpose Food Additive	21 CFR 582.1320
Edetate Disodium USP Dihydrate	Disodium EDTA	FDA has no questions regarding intended use.	GRN000363
Pullulan	Pullulan	FDA has no questions regarding intended use in certain foods.	GRN000099
Tamarindus Indica Seed Polysaccharide	Tamarindus Indica Seed Polysaccharide	FDA has no questions regarding intended use.	GRN000503
Isomalt	Isomalt	Self-Determined GRAS (1996)	GRN6G0321
Simethicone USP	Simethicone		
Sodium Hyaluronate	Sodium Hyaluronate		
Poloxamer 407	Poloxamer 407		
Zea Mays (Corn) Starch	Zea Mays (Corn) Starch		
Carbomer	Carbomer		
Water			

CONFIDENTIAL

This document is confidential. Do not disclose or use except as authorized.

11.1.2 Compatibility

N/A

11.1.3 Handling

There are no special handling requirements.

11.1.4 Availability

Compound dexamethasone solution in Mucolox™ will be dosed at a concentration of 0.5 mg/5mL and dispensed through the BWH Investigational Pharmacy. The prescription for the patients in ARM B (dexamethasone) will also be dispensed through the BWH Investigational Pharmacy.

11.1.5 Preparation

Study subjects will be given a kit with the following, including detailed written instructions (see Appendix 1):

ARM A

- A four week supply of compound dexamethasone solution in Mucolox™ will be dispensed, with extra for error and spillage, which will be rounded to 480 mL bottle at a concentration of 0.5 mg/5mL.
- Small dosing cups

11.1.6 Administration

Subjects will be instructed to rinse with 5 ml of compound dexamethasone solution in Mucolox™ (0.5 mg/5ml; ARM A) for 5 minutes. After 5 minutes, subjects will be instructed to expectorate and to not eat or drink for 15 minutes after. The rinses will be completed three times per day, equally spaced during awake hours. If a study rinse is missed, subjects will be asked to attempt to make up for the missed rinse later the same day, to maintain four rinses per day. If necessary, for example, two consecutive 5-minute rinses can be completed at night before bed. This does not pose any known safety risk.

11.1.7 Ordering

Study rinses will be ordered through the BWH Investigational Pharmacy via EPIC.

11.1.8 Accountability

A study diary will be given to the subject where they will be asked to check off each rinse completed, with three check boxes per day on study (Appendix 2).

CONFIDENTIAL

This document is confidential. Do not disclose or use except as authorized.

11.1.9 Destruction and Return

[figure not shown]
Patients should not continue to use any unused study supply once they have completed the study. It should be returned to the investigator and will be sent to pharmacy for destruction.

11.2 Dexamethasone solution

11.2.1 Description

Dexamethasone (NDC 00054-3177-63; Roxane Laboratories, Columbus, OH 43216-6532) is a synthetic adrenocortical steroid commercially available as a 0.5mg/5mL solution. It is stable in air and practically insoluble in water.

- The molecular weight is 392.47.
- The molecular formula is $C_{22}H_{29}FO_5$
- The structural formula is:

Each 5 mL of oral solution contains 0.5 mg of dexamethasone and citric acid, disodium edetate, flavoring, glycerin, methylparaben, propylene glycol, propylparaben, sorbitol and water.

